1.0 Objectives

1.1 Study Objectives

Describe the purpose, specific aims or objectives. State the hypotheses to be tested.

Aim 1: Pilot test the effect of Smart Ambient Bright Light (SABL) in reducing agitation in persons with dementia. We will also examine the effect of SABL on other Behavioral and Psychological Symptoms of Dementia (BPSD), affect, and sleep and side effects. We hypothesize that participants will show less agitation and other BPSD and improve affect and sleep during and after SABL compared to baseline and control periods. We will also explore the intervention effect on residents' other behavioral and psychological symptoms and affect and monitor potential side effects.

Aim 2: Evaluate the fidelity of the SABL delivery. We will evaluate the fidelity of SABL delivery. We will measure lighting intensity (lux) and circadian stimulus (CS) levels via two methods: 1) on-site light measurements, and 2) a personal light monitor. We will compare the actual lighting dosage to our target lighting dosage.

Aim 3: Evaluate the feasibility of implementing the SABL. We will use convergent mixed methods to evaluate the acceptability, feasibility, and appropriateness of the interventions from perspectives of nursing home staff and administrators.

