7.1 Study Design

Describe and explain the study design.

Aim 1: Pilot test the effect of SABL in reducing agitation in persons with dementia. This is a crossover, cluster randomized control trial to pilot test the effect of SABL in NHs. This design includes a 4-week intervention period and 2-week washout period. This design will allow for participants to act as their own control and thus reduce the needed sample size and strengthen the research rigor. The study procedures include five phases over 13 weeks. We will recruit a total sample of 40 nursing home residents with dementia and agitation from the 2 nursing homes, 20 residents from each nursing home. The two NHs will be randomly assigned into different sequences for intervention and control. Otherwise, the same study procedures will be

conducted simultaneously at the two NHs. During the daytime, participants will be guided and encouraged to spend time in the designated areas in the dining room and activity room for their meals and daily activities. For blinding prior to control period, we will perform installation procedures with non-SABL light bulbs. We will evaluate the effect of SABL on agitation, other BPSD, affect, and sleep, based on the actual lighting levels participants receive measured by personal light monitors. The study procedures include five phases: 1) baseline, 2) intervention, 3) post intervention/washout, 4) control, and 5) post control/washout. The sequence of intervention and control differs between the two NHs based on randomized assignment. Agitation and lighting will be measured at baseline and then once every two weeks throughout the study. We hypothesize that participants will show less agitation during and after SABL compared to baseline and control periods. We will also explore the intervention effect on other BPSD and affect and monitor adverse effects. **Aim 2: Evaluate the fidelity of the SABL delivery.** We will evaluate the fidelity of SABL delivery by measuring lighting intensity (lux) and CS levels in two ways: 1) on-site light measurements, and 2) a personal light monitor. The actual lighting data will be compared to the intended SABL design.

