- 1) Data extraction from CMS Nursing Home Compare Website (<https://www.medicare.gov/care-compare/>): Data on facility characteristics, including number of certified beds, ownership, quality rating, participation in Medicaid, staffing, COVID-related data is publicly available and can be accessed through the link provided above.
- 2) Chart reviews: Data on resident characteristics, including age, race, sex, diagnoses, level of cognitive impairment, current medication use, current listed comorbidity and physical function, BPSD in the past two weeks, pain in the past two weeks, current vision status, current hearing status, and other clinical conditions.
- 3) Surveys based on staff caregivers' reports: The surveys will be conducted on paper and in-person with researcher administering the survey to the staff caregiver for proxy report of residents' dementia stage, agitation, other BPSD, affect, and side effects.
- 4) Personal light monitor, LYS button, placed on individual resident participants to measure lighting intensity (lux) and CS levels participants receive.

There will be seven visits for data collection throughout the 13-week of the study: baseline visit (week 1) and six follow-up visits, every other week (weeks 3, 5, 7, 9, 11, 13). The procedures for each visit are as follows:

Baseline visit: Procedures 1 through 4.

Follow-up visits: Procedures 3 and 4.

For the procedure 4, the light monitor will be worn 7 days a week during the data collection weeks (week 1, 3, 5, 7, 9, 11, & 13).

Aim 2: We will evaluate the fidelity of SABL delivery by measuring lighting intensity (lux) and CS levels.

Data collection procedures will include the following:

- 1) on-site manual light measurements
- 2) personal light monitor, LYS button, placed on individual resident participants (same as the procedure 4 in aim 1).

The procedures will be conducted primarily on site at the nursing home facilities.

The procedure 1 will be conducted twice a week throughout the 13-week study period.

For the procedure 2, as mentioned in aim 1, the light monitor will be worn 7 days a week during the data collection weeks (week 1, 3, 5, 7, 9, 11, & 13).

Aim 3: Staff and Administrators

Data collection methods include the following:

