7.3 Duration of Participation

Describe how long subjects will be involved in this research study. Include the number of sessions and the duration of each session - consider the total number of minutes, hours, days, months, years, etc.

Aims 1 and 2: Residents

The study lasts 13 weeks with baseline data collection: one week for baseline, four weeks for intervention (SABL), two weeks for post intervention/washout period, four weeks for control, and two weeks for post control. The baseline survey of the residents regarding cognitive function and agitation may take 10 minutes to complete.

Aim 3: Staff and administrators 1-2 visits for a total of 1-2 hours. The surveys will take approximately 10-15 minutes to complete, and the interview will take about 1 hour.

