7.4.3 Method for Assigning Subject to Treatment Groups

Describe the randomization process and how the associated treatment assignment will be made.

The study design is a crossover, cluster randomized controlled trial. We plan to conduct the study in two nursing homes. The study procedures include five phases over 13 weeks (Table). The two NHs will be randomly assigned into different sequences for intervention and control. Otherwise, the same study procedures will be conducted simultaneously at the two nursing homes. During the daytime, participants will be guided and encouraged to spend time in the designated areas in the dining room and activity room for their meals and daily activities.

Table. Intervention testing procedures and timeline.

Week	1	2	3	4	5	6	7	8	9	10	11	12	13
------	---	---	---	---	---	---	---	---	---	----	----	----	----

Study phases	NH A	Baseline	Intervention		Post intervention/washout		Control			Post control	
	NH B		Control		Post control/washout		Intervention			Post intervention	
Lighting	Usual light		I: SABL C: Usual light		Usual light		C: Usual light I: SABL			Usual light	
Data collection	Baseline, L&E		L&E	L&E		L&E		L&E	L&E		L&E

L=lighting measured via individual light monitor, E=effect outcomes (e.g., agitation, BPSD, affect, and sleep) and adverse effects

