8.3 Statistical or Analytic Methods

Describe the statistical methods (or non-statistical methods of analysis) that will be employed.

Aim 1

All data will initially be assessed with descriptive techniques to determine distributions and identify outliers. Baseline to post-intervention changes in participants' CMAI, NPI-NH, and ARS scores will be used as the outcomes in all subsequent analyses. To conduct the group analysis, each participant will serve as their own control, which allows minimal use of control variables. The effect of the intervention will be analyzed using multi-level modeling to adjust for clustering of participants at the facility level. We will use the daytime and nighttime average of lighting dosages (lux and CS) from the personal light monitors as the independent variable to analyze the effect of SABL on changes in CMAI, NPI, and ARS. Although not powered for a detailed analysis, we will explore the impact of participant characteristics (sex, age, race, ethnicity, ADRD stage, and daylight exposure) on the intervention effect by adding them as covariates to the regression model.

Aim 2

All data will initially be assessed using descriptive techniques to examine underlying assumptions and detect any violations. To assess the intervention fidelity, the lux and CS data measured via manual measurements will be analyzed using one sample t-tests to analyze lighting levels during the day and nighttime, compared to the target levels. The data from personal light monitors will be analyzed similarly at individual level. Although not powered for a detailed analysis, we will explore the impact of participant characteristics (e.g., sex, age, race, dementia stage, comorbidity, facility, and daylight conditions) on the lighting received based on the personal light monitor.

Aim 3

Quantitative Analysis: The data include ratings of acceptability, feasibility, appropriateness, time, and cost of installing and maintaining the intervention. All data will be analyzed using descriptive analyses. Although not powered for a detailed analysis, we will explore differences in perceptions of intervention feasibility and acceptability between sexes as well as the difference across professional roles and between facilities.

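### The 'after SABL' comparison is set against baseline and the control period, which fall in different weeks; the calendar-matched post-control phase is measured but not named as its comparator

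*Protocol*

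**What the plan says.** Protocol 7.1 gives the Aim 1 hypothesis: "We hypothesize that participants will show less agitation during and after SABL compared to baseline and control periods". Section 1.1 uses the same comparators for the other resident outcomes: "improve affect and sleep during and after SABL compared to baseline and control periods".

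Section 7.1 lists control and post-control as separate phases: "1) baseline, 2) intervention, 3) post intervention/washout, 4) control, and 5) post control/washout". Section 7.3 gives the phase lengths: "one week for baseline, four weeks for intervention (SABL), two weeks for post intervention/washout period, four weeks for control", followed by two weeks of post-control. Section 7.2 schedules a "baseline visit (week 1) and six follow-up visits, every other week (weeks 3, 5, 7, 9, 11, 13"). The homes take opposite orders on one calendar (7.4.3): "Otherwise, the same study procedures will be conducted simultaneously at the two nursing homes".

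On analysis, 8.3 and the SAP share one sentence: "Baseline to post-intervention changes in participants' CMAI, NPI-NH, and ARS scores will be used as the outcomes in all subsequent analyses". Both add multilevel modelling for facility clustering, with measured light dose as the independent variable. Neither states a week, period or sequence term, or a contrast between post-SABL and post-control.

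**The concern.** The hypothesis has two halves, during and after SABL, and gives both the same comparators. The crossover balances calendar time for one of the resulting comparisons only: during SABL against the control period. After SABL is balanced against neither comparator, and during SABL is not balanced against baseline.

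Anything that moves agitation in both homes over the 13 weeks, such as study attention, season, rater habituation or disease course, therefore enters the after-SABL estimate. Shared improvement would look like lasting benefit, and shared worsening would hide it. Comparisons with baseline are also open to regression to the mean, because entry depends on a CMAI threshold of 45 (3.1, 4.2.4) and CMAI is the outcome scale.

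The light-dose predictor does not repair this. Post-SABL and post-control are both under usual light in Table 1, so dose measured in those weeks cannot identify an effect that outlasts the light.

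**Working it through.** **Inputs.** Visit weeks and phases come from Table 1 and 7.2. The final sample of 36 (taken as 18 per home) and d = 0.53 come from 8.2. The plan gives no figure for shared change or for within-resident correlation, so both are assumed. The 0.53 serves only as a reference size. (The power of 0.92 in 8.2 is reproduced within 2 points by a one-sided paired t with n = 36, 0.930, or a two-sided normal approximation with n = 40, 0.918. A two-sided paired t with n = 36 gives 0.871.)

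**Step 1: visit weeks.**

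| Phase | NH A | NH B | Mean week |
|---|---|---|---|
| Baseline | 1 | 1 | 1 |
| SABL | 3, 5 | 9, 11 | 7 |
| Control | 9, 11 | 3, 5 | 7 |
| Post-SABL | 7 | 13 | 10 |
| Post-control | 13 | 7 | 10 |

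**Step 2: calendar offset of each contrast, in weeks.**

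| Contrast | NH A | NH B | Mean |
|---|---|---|---|
| Post-SABL − baseline | 7 − 1 = +6 | 13 − 1 = +12 | +9 |
| Post-SABL − control | 7 − 10 = −3 | 13 − 4 = +9 | +3 |
| Post-SABL − post-control | 7 − 13 = −6 | 13 − 7 = +6 | 0 |
| SABL − control | 4 − 10 = −6 | 10 − 4 = +6 | 0 |
| SABL − baseline | 4 − 1 = +3 | 10 − 1 = +9 | +6 |

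A shared linear change of total size T over weeks 1 to 13 leaves a bias of T × (mean offset)/12: 0.75T for post-SABL versus baseline, 0.25T versus the control period, 0 versus post-control, and 0.5T for during SABL versus baseline.

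**Step 3: illustrative error rates.** The simulation assumes no SABL effect, total SD 1, correlation 0.5, independent residents and no home-by-period effect. Tests are two-sided at 0.05: a paired t on 36 differences and a t stratified by home. Ranges span the two tests.

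| Shared improvement T | 0.25 SD | 0.53 SD | 0.80 SD |
|---|---|---|---|
| Post-SABL vs baseline: bias | 0.19 | 0.40 | 0.60 |
| Post-SABL vs baseline: false-positive rate | 19% | 64% | 93% |
| Post-SABL vs control: bias | 0.06 | 0.13 | 0.20 |
| Post-SABL vs control: false-positive rate | 6–7% | 13–15% | 21–27% |
| Post-SABL vs post-control: false-positive rate | ≤ about 5% | ≤ about 5% | ≤ about 5% |
| During SABL vs baseline: false-positive rate | 13% | 42% | 76% |

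At correlation 0.7 and T = 0.53 SD, the paired test gives 84% against baseline and 17% against the control period.

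**Step 4: other shapes of change.** A one-off drop just after week 1 biases only the comparisons with baseline. A change confined to weeks 12–13 puts half its size into both after-SABL comparisons the plan names, and none into post-SABL versus post-control.

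**Step 5: price of the balanced comparator.** At correlation 0.5 the variance of a within-resident difference is 0.5 + 0.5 = 1.00 against one post-control visit, and 0.5 + 0.25 = 0.75 against the mean of two control visits. The standard error ratio is √(1.00/0.75) = 1.15.

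If a benefit of 0.53 SD persisted fully, NH A's week 7 minus week 13 would be 0 and NH B would keep 0.53, so the average is 0.53/2 = 0.265. With n = 36 the standardised effect falls from 0.53/(1/6) = 3.18 to 1.59, and power from about 87% to 34%. Against the control period, whose NH A visits (weeks 9 and 11) also follow SABL, it falls from 0.53/(0.866/6) = 3.67 to 1.84, and power from about 95% to 43%.

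**The case against.** Five points on the other side have weight.

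- **The rates are not those of a planned test.** A reader might infer that the trial will run a test with a 64% error rate. The documents do not support that: 8.3 and the SAP specify a multilevel model with light dose as predictor. The percentages show how far shared change could distort the stated comparisons.
- **The direction is unknown.** It is tempting to say that shared change would be counted as lasting benefit. No document gives a trend or its sign, so worsening that masks a benefit is equally possible.
- **The baseline problem is not peculiar to the after-SABL half.** One might infer that the crossover protects everything measured during SABL. It does so only against the control period. The part specific to the after-SABL half, the comparison with the control period, is modest: the error rate reaches about twice alpha only when shared change is near 0.53 SD.
- **The phrase control periods is somewhat ambiguous.** Table 1 gives both phases usual light, so a loose reading could include post-control. But 7.1 and Table 1 list the phases separately and the SAP does not settle it. The text does not expressly exclude post-control; it leaves the comparator unstated.
- **The remedy is weakest when persistence is strongest.** This is true and should be disclosed. It does not favour the control period, which suffers the same dilution. Baseline is the only comparator in NH A free of carryover, which is a reason to keep reporting it.

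Aim 1 is a pilot, which lowers the stakes. Even so, it states a directional hypothesis, and 2.3 says the findings will inform future studies.

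**Conclusion.** The point holds. As written, the after-SABL comparison is open to any change shared by the two homes, in either direction: 9 weeks' worth on average against baseline and 3 weeks' worth against the control period. These offsets follow from Table 1 alone. The error rates depend on an assumed linear trend, a correlation of 0.5 (0.7 as a check) and independent residents.

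Adding week effects while keeping the stated comparators would not be enough. No control-period or baseline visit falls in week 7 or 13 in either home, so with a free effect for each week, post-SABL versus either comparator cannot be separated from time. Post-SABL versus post-control can be, because each of those weeks contains one phase in each home.

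The gain has a limit. With one home per sequence, only change common to both homes is removed; home-specific change over time stays confounded under any contrast.

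**What to change.** - **Protocol 1.1 and 7.1:** split the hypothesis into (a) during SABL versus the control period and (b) after SABL versus the post-control phase.
- **Protocol 8.3 and SAP:** estimate both within resident, weighting the two homes equally. For (b) this is week 7 minus week 13 in NH A and week 13 minus week 7 in NH B. The multilevel model can do the same with phase contrasts and week effects.
- **Changes from baseline:** report them for both the during and after phases, labelled supportive and uncontrolled for time.
- **State the limits:** the dilution of (b) if benefit remains in NH A at week 13, the equivalent dilution against the control period, and the confounding of home-specific change.
- **Section 7.2.2:** it describes visits 2–6 only. Align it with the six follow-up visits in 7.2, because (b) needs week 13.

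The cost is wording and analysis specification; weeks 7 and 13 are already scheduled in both homes. The statistical price is a standard error about 15% larger for (b) than against the mean of two control visits, and up to half the effect lost under full persistence.

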1.2 Primary Study Endpoints

State the primary endpoints to be measured in the study.

Research typically has a primary objective or endpoint. Additional objectives and endpoints are secondary. The endpoints (or outcomes), determined for each study subject, are the quantitative measurements required by the objectives. Measuring the selected endpoints is the goal of a trial (examples: response rate and survival).

The primary outcomes of this study are 1) the effect of SABL on residents' agitation, other BPSD, affect, sleep and any side effects, 2) fidelity of SABL (e.g., lighting level on site and at individual level), and 3) feasibility of implementing SABL (e.g., acceptability, feasibility, appropriateness, time, and cost of implementing and maintaining the lighting).

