- 1) Surveys: Surveys will be administered to staff in-person and on paper to collect their characteristics (e.g., age, race, gender, education, & professional experiences) and their evaluation on the acceptability, feasibility, and appropriateness of the SABL lighting intervention.
- 2) Qualitative interviews: Staff's and administrators' inputs on the acceptability, feasibility, and appropriateness of the SABL lighting intervention.
- 3) We will also calculate the total hours and cost of installing and maintaining the SABL.

The procedures can be conducted either in person at the facility or via virtual conference (e.g., zoom). The procedure will be conducted in one visit scheduled in week 13.

Table 1. Intervention testing procedures and timeline.

Week		1	2	3	4	5	6	7	8	9	10	11	12	13
Study phases	NH A	Baseline	Intervention			Post intervention/washout			Control			Post control		
	NH B		Control			Post control/washout			Intervention			Post intervention		
Lighting		Usual light	I: SABL C: Usual light			Usual light			C: Usual light I: SABL			Usual light		
Data collection		Baseline, L&E		L&E		L&E		L&E		L&E		L&E		L&E

L=lighting measured via individual light monitor, E=effect outcomes (e.g., agitation, BPSD, affect, and sleep) and adverse effects

Table 2 Summary of Variables, Measures, and Data Collection.

Aim	Variables	Measures	Data collection methods	Timing
Aim 1	Facility characteristics	# of certified beds, ownership, quality rating, participation in Medicaid, staffing, COVID-related data.	CMS Medicare NH Compare Rating System.	Baseline.
	Resident characteristics	Age, race, sex, diagnoses, medication use, comorbidity, physical function, pain, vision, and dementia stage based on CDR.	Data extraction from medical records and MDS. CDR ratings will be measured via inputs from staff caregivers (e.g., nurse or CNAs).	
	Agitation, BPSD, affect, sleep & adverse effects	CMAI, NPI-NH, ARS, sleep & adverse events checklist.	Inputs from staff caregivers (e.g., nurse or CNAs) based on participants' conditions in past week.	Baseline & every two weeks.
Aims 1 & 2	Light level (lux & CS).	Lighting level each participant receives.	Personal light monitor, LYS button, every 10 minutes, 24 hours/day, 7 days/week.	
Aim 2	Light level (lux & CS).	Lighting level SABL delivers.	Manual on-site measurements.	Baseline & twice a week.
Aim 3	NH employee characteristics	Age, race, gender, education, & professional experiences.	Surveys.	Week 13.

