- The test finding is accompanied by clinical symptoms. We will not be able to completely distinguish whether a clinical symptom is resulted from dementia or other comorbidities, or it is resulted from the SABL treatment. We will assess dementia-related symptoms, including behavioral and psychological symptoms at baseline and every other week throughout the 13-week study period. Also, during the 13-week study period, the SABL will only be provided for 4 weeks. When a clinical symptom occurs during those 4 weeks, we will compare the participant's symptoms with the baseline and non-intervention period to examine if the symptoms are possibly SABL-related. In addition, we will examine other comorbidities that may contribute to the clinical symptoms, such as delirium, urinary tract infection, and a new medical condition/procedure that may cause pain (e.g., tooth extraction, fall). We will collect all relevant information and document it and will observe if the same symptom occurs to other participants.
- The test finding necessitates additional diagnostic evaluation(s) or medical/surgical intervention; including significant additional concomitant drug treatment or other therapy.

NOTE: Simply repeating a test finding, in the absence of any of the other listed criteria, does not constitute an adverse event.

- The test finding leads to a change in study drug dosing or discontinuation of subject participation in the clinical research study

The test finding is considered an adverse event by the investigator.

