19.1.2 Safety Monitoring

Include this section if FDA regulations apply to this study (see "WORKSHEET: Drugs (HRP-306)" and "WORKSHEET: Devices (HRP-307)". HRP-306 and HRP-307 can be accessed by clicking the Library link in CATS IRB (<http://irb.psu.edu>).

Indicate the process for identifying, recording, and reporting adverse events.

Specify roles for adverse event recording and monitoring. Indicate each staff member's role in the adverse event reporting process. Include the following if applicable:

The Principal Investigator will confirm that all adverse events (AE) are correctly entered into the AE case report forms by the coordinator; be available to answer any questions that the coordinators may have concerning AEs; and will notify the IRB, FDA, sponsor and/or DSMB of all applicable AEs as appropriate. All assessments of AEs will be made by a licensed medical professional who is an investigator on the research.

The Research Coordinator will complete the appropriate report form and logs; assist the PI to prepare reports and notify the IRB, FDA and/or DSMB of all Unanticipated Problems/SAE's.

The **Monitor** will confirm that the AEs are correctly entered into the case report forms. The Monitor will also confirm that the adverse events are consistent with the source documents and are reported to the appropriate regulatory bodies as required.

During the 13 weeks of lighting intervention, the research team will identify adverse events through interviews with CNAs using a checklist, which includes deteriorated BPSDs, skin rash, eye irritation, dizziness, nausea, or any other reactions. Data will be collected routinely once every two weeks throughout the study period or as needed by staff reporting. If there is a report of adverse events, PI [name] will ensure that these adverse events are correctly logged and entered into the AE case report forms and notify the IRB, FDA, and NIH. The research coordinator will keep track of the adverse event and assist PO [name] to prepare reports to notify IRB, FDA, and NIH.

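### The side-effect checklist looks back one week but is given every two weeks, so as written it asks about 14 of the 28 SABL days and short-lived events may be undercounted in both conditions

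*Protocol*

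**What the plan says.** Section 1.2 of the Protocol names as its first primary outcome "the effect of SABL on residents' agitation, other BPSD, affect, sleep and any side effects".

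Table 2 in section 7.2 handles these measures in a single row: "CMAI, NPI-NH, ARS, sleep & adverse events checklist". Staff caregivers supply the answers "based on participants' conditions in past week", with timing "Baseline & every two weeks". Section 7.2 places the visits in weeks 1, 3, 5, 7, 9, 11 and 13.

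Sections 7.2.2 and 19.1.2 repeat the two-week rhythm without giving a look-back. Section 19.1.2 adds one further route: "Data will be collected routinely once every two weeks throughout the study period or as needed by staff reporting". Section 18.2 notes that "during the 13-week study period, the SABL will only be provided for 4 weeks" and sets out how a symptom is to be judged: "When a clinical symptom occurs during those 4 weeks, we will compare the participant's symptoms with the baseline and non-intervention period".

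The SAP contains nothing on how adverse events are collected or analysed.

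**The concern.** A past-week window suits a severity scale such as the CMAI, where each visit samples the resident's current state. It does not suit event capture, where the aim is to account for the whole period of exposure. A seven-day look-back repeated every fourteen days leaves seven days of each cycle that no visit asks about.

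The effects on the checklist in section 19.1.2 include skin rash, eye irritation, dizziness and nausea, any of which may be brief. One that begins and ends within an uncovered week is recorded only if a staff member volunteers it. Chart review will not routinely recover it, because section 7.2 schedules that procedure at baseline only. Section 9 (data and safety monitoring) is marked not applicable, so the checklist is the main systematic source of safety data.

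At stake is how far a finding of few or no side effects can be trusted. Section 2.2 itself criticises earlier light studies for saying little about side effects.

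**Working it through.** **Inputs**
- Look-back: 7 days (Table 2).
- Visits: weeks 1, 3, 5, 7, 9, 11, 13 (section 7.2).
- Phases: 1 + 4 + 2 + 4 + 2 = 13 weeks (section 7.3). SABL therefore runs in weeks 2–5 at NH A and weeks 8–11 at NH B, with control in the opposite block.

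**The plan's own figure.** Every other week from 1 to 13 gives (13 − 1)/2 + 1 = 7 visits, as section 7.2 states.

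**Days covered.** Number the SABL days 1 to 28 and take interviews at the end of the visit week. At NH A, the visits in weeks 3 and 5 cover days 8–14 and 22–28. At NH B, the visits in weeks 9 and 11 cover the same day numbers. Covered: 7 + 7 = 14 of 28 = 50%. Days 1–7 and 15–21 lie in no window.

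With interviews at the start of the visit week, days 1–7 and 15–21 are covered instead. Days 8–14 and 22–28 are not, because the next visit reaches back only into the week after SABL ends. A day count over every weekday of visit, with the visit day included or excluded, gave 14 of 28 at both homes each time. The control block is also four weeks with two visits in the same positions, so it too has 14 of 28.

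Over the whole study, end-of-week interviews cover 7 of 13 weeks. Start-of-week interviews cover 6, because the first window then falls before week 1.

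**Illustrative share of events missed by the checklist.** Assume onset uniform over the 28 days and end-of-week interviews. An event lasting L days (L ≤ 7) is missed if it starts and ends inside one uncovered week. That allows 8 − L start days in each of two weeks:

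missed = 2 × (8 − L) / 28

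| Duration L | Start days missed | Share missed |
|---|---|---|
| 1 day | 14 of 28 | 50% |
| 3 days | 10 of 28 | 36% |
| 5 days | 6 of 28 | 21% |
| 7 days | 2 of 28 | 7% |
| 8 days or more | 0 of 28 | 0% |

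These shares are before any spontaneous staff report.

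**Dependence on uniform onset.** If effects cluster in the first days of new light, the interview day matters. For a 3-day event starting on days 1–5, end-of-week interviews miss all and start-of-week interviews miss none. The documents do not fix the interview day.

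**After the change.** With a look-back to the previous visit (14 days), coverage is 28 of 28 SABL days at both homes for every visit day.

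**The case against.** The strongest reply is that the one-week look-back appears only in a pooled cell of a summary table. The sections that govern adverse events (18.2 and 19.1.2) give no window, and the checklist is not in the documents because the template keeps data collection materials out of the protocol. The sponsor may intend full coverage. This stands as a limit on certainty. It does not remove the point, since the only window stated is one week.

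A second reply is that the off weeks are not unwatched. Staff may report as needed, the team is on site twice a week for light measurement, and section 18.2 speaks of biweekly site visits to monitor adverse events. The first is a real route, but a passive one. No adverse-event enquiry is stated for the light-measurement visits. Biweekly could mean twice a week, but section 19.1.2 sets routine collection at once every two weeks. Nor should staff reports be dismissed: section 7.4.25 limits what staff are told about the design and the lighting sequence, to protect blinding, and does not say that they are kept unaware of possible side effects.

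A third reply is that persistent or recurrent effects would reach a covered week. That is correct, and the table above shows it.

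A reader might also infer that the gap tilts the comparison towards SABL. The documents do not support this. Control weeks have the same 50% coverage, and section 18.2 judges relatedness by comparing SABL weeks with baseline and non-intervention weeks.

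**Conclusion.** The point holds in a limited form. As Table 2 is written, systematic enquiry about side effects reaches 14 of 28 SABL days at each home and 14 of 28 control days. Short-lived events may therefore be undercounted in both conditions unless staff volunteer them. The day count needs only the stated window, the stated visit weeks and a constant visit day. The shares missed, from 50% at one day to none at eight days or more, also rest on uniform onset and on no spontaneous reporting.

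A reader might go further and conclude that half of all side effects will be lost, or that SABL would be wrongly declared free of them. Neither follows. The documents give no event durations or reporting rates, so the size of any undercount is unknown. The consequence that does follow is lower absolute counts, and weaker support for any statement that SABL had few or no side effects. For a listed primary outcome, that justifies a change costing almost nothing.

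**What to change.** In Table 2 and section 19.1.2, separate the adverse events checklist from the symptom scales and give it its own look-back: *since the last study visit*. For each event, record the onset date and whether it is ongoing, and report events by phase of onset. Keep the past-week window for the CMAI, NPI-NH, ARS and sleep.

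The onset date is needed because a two-week look-back can straddle a change of phase. With start-of-week interviews, for example, the week 7 visit reaches back over weeks 5 and 6, and at NH A week 5 is SABL and week 6 is washout.

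The cost is a line in Table 2, a matching line in section 19.1.2 and a few words on the checklist, with no new visit, instrument or staff. The downside is that two-week staff recall is somewhat less exact than one-week recall. If the sponsor already intended full coverage, the same edit serves as the clarification.
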